The goal of this proposal is to conduct a prospective randomized controlled phase III study comparing Rituximab (RTX) to Cyclosporine (CSA) in the treatment of patients with IMN. Once a patient with IMN and proteinuria $\geq 5\text{g}/24\text{h}$ is identified, meets other entry criteria and consents to the study, he/she will receive a minimum of 3 months of conservative therapy aimed at maximizing Angiotensin II blockade (run-in phase). If at the end of this period the patient still meets entry criteria he/she will be randomized into a 12-month treatment period, and a subsequent follow-up of 12 months. Efficacy of treatment will be assessed by remission status (based on changes in proteinuria) at 24 months from randomization. Patient safety will be assessed via collection of adverse event data and evaluation of pre- and post-treatment laboratory data. At the 6-month post-randomization visit, patients who have been randomized to either CSA or RTX but who do not have a reduction in proteinuria $\geq 25\%$ (confirmed on repeat measurements within 2 weeks) will be considered treatment failures and exit the study. Data from that point onward will be censored. Patients in the RTX group who have a reduction in proteinuria of equal to or $>25\%$ at 6 months will be given another identical course of RTX (1g x 2). This treatment regimen was chosen given our initial data that suggested a percentage of our cohort appeared to respond to an additional course of therapy. Data from our 2 pilot studies showed that RTX is out of the circulation by month 2 in the majority of patients and B cells have recovered by month 3 in patients treated with RTX 1g x 2 (the regimen chosen for the study). Thus, at 6 months, patients in the RTX arm are completely, at least as best as we can measure, free of immunosuppression, and hence the second course should not be associated with additive toxicity. The same definition of response will apply to the CSA arm at 6 months. An equal to or $>25\%$ reduction in proteinuria will dictate continuation of the CSA for an additional 6 months (total of 12 months of full dose CSA). This assessment at six months allows a balance between risk-benefit in both arms. The protocol provides similar exposure to immunosuppression in both arms and allows an early exit for patients related to safety issues by providing a lack of efficacy (futility) end point at 6 months.

Primary endpoint

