For those patients in the Cyclosporine arm, **Cyclosporine trough level measurements will be done every 2 weeks +/- 3 days after initiation of Cyclosporine until levels are stable and at target. Potassium and creatinine will also be checked in conjunction with CSA level. If Cyclosporine dose is changed during treatment, potassium, creatinine and CSA level will be rechecked every 2 weeks +/- 3 days until levels are stable and at target.** Cyclosporine levels will also be assessed whenever serum creatinine rises by $>30\%$ without a recognizable reason such as volume depletion, additional drugs, sepsis, etc. Patients who cannot tolerate the medications and/or who are treatment failures at 6 months will exit the study at 6 months (i.e., the 6 month visit and accompanying data collection should still occur). Patients who go in to complete remission will discontinue study drug but will continue with full visit follow-ups until month 24 as scheduled. However, the therapeutic/management plan for these patients will be solely at the discretion of the managing nephrologist although while in CR no further immunosuppressive therapy is recommended. Likewise, patients who relapse from either a partial or complete remission or who are not in partial or complete remission by the end of the treatment period (i.e., 12 months) will continue with the visit schedule, but the therapeutic/management plan will be solely at the discretion of the managing nephrologist. Finally, for patients who temporarily stop taking Cyclosporine, there are three possible scenarios:

1. Patients who discontinue Cyclosporine for < 2 weeks may simply be restarted on the study drug and continue to fully participate in the trial. The treatment is to be restarted at its former dose and the patient returned to the regularly scheduled follow-ups including the periodic sampling for assessing potassium, creatinine and CSA trough levels.
2. Patients who discontinue Cyclosporine for ≥ 2 weeks, but < 4 weeks may also be restarted on the study drug at its former dose and fully participate in the trial, but the temporary discontinuance will be logged as a protocol deviation and the missed treatment days will be made up at the end of month 12. This is to ensure that all patients receive approximately 12 months of treatment with study drug.

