3. Patients who discontinue Cyclosporine for ≥ 4 weeks will not be restarted on study drug, but will continue with full visit follow-ups until month 24 as scheduled. The therapeutic/management plan will be solely at the discretion of the managing nephrologist.

Laboratory testing

In order to contain costs all clinical tests will be carried out locally at the recruiting centers. However, at critical time points: Time 0, and 6, 12, 18, and 24 months from start of treatment, recruiting centers will ship to Mayo Clinic, Rochester, Minnesota, 2 blood samples and 2 urine samples (aliquots obtained from two 24h urine collections) for determination of serum creatinines, serum albumins and urinary protein/creatinine ratios. Blood and urine kits will be provided by Mayo Clinic, Rochester, Minnesota, for these

samples along with shipping costs (see Lab Manual). The Central Lab results (Mayo Clinic, Rochester, MN) will be used for statistical purposes since this will ensure a standard methodology is applied to the critical (for the trial analysis) laboratory assessments. By measuring the volume of the 24-hour urine collection we will also be able to calculate both clearance and the 24-hour urine protein from the aliquot. Proteinuria results at Time 0, 6, 12, 18 and 24 months will be taken as the mean of two 24-hour urine collections done back to back (within 14 days of each other), and the mean of these 2 collections will be used to determine CR, PR, or NR.

In order to control for the possibility of under collection or over collection of urine, a maximum 20% variation in total 24h urine creatinine (mg/specimen) will be allowed between the two urine collections required at Time 0, 6 months, 12 months, 18 months, and 24 months. A difference of greater than 20% will necessitate a third urine collection (also to be sent to the central lab), with the values from one of the two previous collections being discarded. We will use the subject's weight to approximate the expected total urine creatinine (mg/kg) to determine which of the previous collections is closest to the truth and which should be discarded. It is anticipated that a 3rd urine collection will be needed in <10% of cases. Proteinuria will be calculated as the mean of these two 24-hour urine collections.

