After the second course of RTX therapy at six months they will have no further RTX therapy regardless of their proteinuria level
3. Significant potential life threatening infection.
4. Persistent elevation of liver enzymes >2 x normal (despite CSA arm dose reduction).
5. Persistent elevation of serum potassium >6.0 mEq/l despite diet changes, ACEi/ARB reduction, diuretic dose increase (and in the CSA arm dose reduction).
6. A rise in serum creatinine by $>30\%$ above baseline that persists in the absence of secondary causes such as volume depletion or use of potential nephrotoxic agents (and despite adjustments in the CSA dose)
7. Persistent hypertension in either arm, i.e. supine blood pressure >160 mmHg systolic or >90 mmHg diastolic, despite institution of maximum antihypertensive therapy (and despite adjustments of CSA dose)

8. Other clinically relevant adverse effects not resolved by reduction in dosage of test medications.
9. Development of any malignancy or lymphoproliferative disorder.
10. Pregnancy.
11. The appearance of an independent disease whose standard therapy requires continuous administration of significant amounts of corticosteroids, other immunosuppressive agents or plasma exchange therapy.
12. Serious concomitant disease with an expected survival of less than 4 years.
13. At the wish of the patient.
14. The study will be placed on hold if 3 of the first 5 patients enrolled and treated with RTX or CSA develop severe opportunistic infections, or experience Grade 3-4 SAEs.

Patients who choose to discontinue study medication or are withdrawn because of adverse events will be strongly encouraged to continue follow up examination to the study termination.

Ancillary studies:

1. DNA Testing

Recent data show that in patients with membranous nephropathy, mutations in HLA-DQA1 and PLA2R1 alleles are associated with an increased risk for developing membranous nephropathy.⁸⁰ One of these alleles, the PLA2R1, is in fact the gene for the PLA2 receptor. In our pilot studies, ~70% of the patients with membranous nephropathy had antibodies present in circulation against PLA2 receptor.⁷⁷ Thus we would like to evaluate a linkage between the presence of these antibodies and potential genetic mutations in this group of patients. We will ask for the patients consent to further evaluate this linkage by collecting samples of blood to perform additional testing as part of their informed consent form (ICF).

2. Quantitative gene expression analysis

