Adverse events (both patient and event counts) will be tabulated by body system, severity and, for each severity, by investigator-assessed relationship to study drug. Group comparisons for adverse events with 4 or more occurrences will be done using chi-square or Fisher's exact test. The last RTX injection is at 6 months and the tapering of Cyclosporine will be completed by the end of month 14. Hence, the adverse events analyses will focus on events through month 18, allowing these additional months for potential lingering Cyclosporine or RTX complications.

The analysis of the primary endpoint (urine protein failure at month 24) will be intent-to-treat (ITT), and will include all randomized subjects in the analysis. For those without a 24 month visit, the 18 month visit results will be used if available, otherwise they will be assumed to have failed at 24 months. Per protocol (PP) analyses will also be done including only those subjects who receive a full course of study medication and who have a 24 month visit.

Interim analyses: No interim analyses for efficacy will be performed during the trial, however safety data will be compiled and reviewed approximately every six months or at the request of the Data and Safety Monitoring Board.

Investigator and Coordinator Training: In order to make efficient use of funding, annual investigator and coordinator meetings will be coordinated with national nephrology meetings where possible. It is expected that the majority of the training will occur through web-based technology and will be coordinated through the data management and coordinating Center.

The **Data Management and Coordinating Center (DMCC)** is located at the Applied Health Research Center (AHRC) at St. Michael's Hospital/University of Toronto. The DMCC will be responsible for facilitating all aspects of the study planning, training, implementation, data collection and analysis.

The clinical information collected for this study will be stored at the DMCC at the Applied Health Research Centre of St. Michael's Hospital in Toronto, ON, Canada and also sent to a federal data repository held by the Office of Rare Diseases Research (ORDR) and located at the University of South Florida (USF) in Tampa, FL.

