related) of the serious adverse event. The medical monitor [and, if applicable, sponsor] may request further information if necessary and possibly request changes to the protocol or consent form as a consequence of the serious adverse event. A back-up notification system is in place so that any delays in review by the medical monitor beyond a specified period of time are forwarded to a secondary reviewer. The eCRF maintains audit trails and stores data (and data updated) related to any adverse event in the study.

Study Discontinuation

The Study Sponsor, DSMB and local IRBs (at their local site) have the authority to stop or suspend this trial at any time. This study may be suspended or closed if:

- Accrual has been met
- The study objectives have been met
- The Study Investigators believe it is not safe for the study to continue
- The DSMB suspends or closes the trial

Subject Discontinuation

An intent to treat approach will be used. All data acquired prior to termination for the reasons outlined below will be included in the primary analysis unless patient withdraws consent. Every effort will be made to conduct a final study visit with the participant and participants will be followed clinically until, if applicable, all adverse events resolve.

Reasons for subject discontinuation include:

- Withdrawal of consent
- Withdrawal by the participant
- Withdrawal by the investigator
- Intercurrent illness or event that precludes further visits to the study site

Regulatory issues:

1. Inclusion of women: Women make up approximately 30-50% of the population of patients with IMN and are expected to be enrolled in numbers in proportion to this normal distribution.
2. Inclusion of minorities: Individuals of all races and ethnicities are at risk for MN. Based on the ethnic composition of the patients followed at, and referred to the Mayo Clinic the population served will include African-Americans, Asian, and Hispanic subjects proportional to that in the general US and Canadian population. This will ensure adequate enrollment within the different racial groups.

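### The protocol gives conflicting rules on whether a patient who stops for intolerance by month 6 leaves the study or is followed to month 24, and the choice can change that patient's primary-endpoint score

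*Combined protocol and SAP*

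**What the plan says.** Five places bear on a patient who stops study drug because of intolerance.

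- **Patient monitoring and evaluation, exit rule.** "Patients who cannot tolerate the medications and/or who are treatment failures at 6 months will exit the study at 6 months". The month-6 visit is still to take place. The conjunction makes intolerance alone enough for exit.
- **Patient monitoring and evaluation, CSA interruptions.** The list opens "for patients who temporarily stop taking Cyclosporine, there are three possible scenarios". Its third case, 4 weeks or more off drug, is in effect a permanent stop. Those patients "will not be restarted on study drug, but will continue with full visit follow-ups until month 24", with treatment left to the nephrologist.
- **Stopping points for medications.** After a list of toxicity and other reasons for stopping that covers both arms, patients who choose to stop or are "withdrawn because of adverse events will be strongly encouraged to continue follow up examination to the study termination".
- **Subject Discontinuation.** A final visit is to be attempted, and "participants will be followed clinically until, if applicable, all adverse events resolve". No visit schedule is attached, and nothing ranks the other rules.
- **Statistical and Analytical Plan.** The primary analysis is intention-to-treat (ITT) on all randomized patients. If month 24 is missing, month 18 is used; "otherwise they will be assumed to have failed at 24 months".

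Non-response is handled consistently. Patients with less than a 25% reduction in proteinuria at month 6 "will be considered treatment failures and exit the study".

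**The concern.** Two sites could each follow the protocol and give the same patient different primary-endpoint results. One site ends participation at month 6, and the patient becomes an imputed failure. The other keeps the visits going, and the patient is scored on the month-24 urine collections. The trial is open-label, so staff know the arm when they decide which instruction applies.

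Safety data are also at stake. Adverse-event analyses are to focus on events through month 18, and the fourth specific aim compares side-effect profiles. Exit at month 6 removes the scheduled visits from patients who have just shown toxicity. Following existing events until they resolve does not provide visits at which new ones would be picked up.

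**Working it through.** **1. The plan's own figure.** Inputs from Sample size estimation: CSA 45%, RTX 55%, margin 15 points, one-sided alpha 0.025, power 80%. With unpooled variance:

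n = (0.45×0.55 + 0.55×0.45) × (1.960 + 0.842)² / (0.10 + 0.15)² = 62.16, rounded up to 63 per arm.

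This matches the plan. Power at 63 per arm is 80.5%. The conflict does not alter the stated sample size.

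**2. Who is affected.**

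| Patient at month 6 | If exited | If followed |
|---|---|---|
| Less than 25% reduction | failure | failure (exits as a non-responder anyway) |
| Intolerant, at least 25% reduction, not in remission at outcome visit | failure (imputed) | failure (observed) |
| Intolerant, at least 25% reduction, in remission at outcome visit | failure (imputed) | responder (observed) |

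Only the last row changes. The outcome visit is month 24, or month 18 if month 24 is missing. Intolerance that first appears after month 6 cannot trigger a month-6 exit.

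**3. How far the text resolves itself.** In the CSA arm, scenario 3 is mandatory and more specific than the exit sentence, so it can be read as governing, although it is introduced under temporary stops. The CSA dosing text also stops the drug for an unresolved creatinine rise without stating study exit, while it does state exit for less than 25% reduction. In the RTX arm there is no counterpart to scenario 3. The exit sentence stands against the encouragement to stay, and nothing decides between them.

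**4. Size per patient.** 1/63 = 1.59 points.

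**5. Illustration.** The change in an arm's rate under exit is the share stopping for intolerance by month 6 times the share of those stoppers who would have been responders if followed. The documents give neither quantity for this setting. Assumed: 15% of CSA and 5% of RTX patients stop; 39% of CSA stoppers would respond (the CSA-arm rate 12 months after stopping, in the placebo-controlled trial described under Cyclosporine); 55% of RTX stoppers would respond (the whole-arm design rate).

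- CSA loss: 0.15 × 0.39 = 5.85 points (3.7 of 63 patients).
- RTX loss: 0.05 × 0.55 = 2.75 points (1.7 of 63 patients).
- Exit in both arms: RTX minus CSA shifts by 5.85 - 2.75 = **+3.1 points**.
- Exit in RTX only, with CSA followed under scenario 3: 0 - 2.75 = **-2.75 points**.
- Equal stopping and equal response in both arms: **0**.

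With exit in both arms and these response rates, the shift favours RTX only if CSA stopping exceeds RTX stopping by a factor above 0.55/0.39 = 1.41.

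**6. A second set of assumptions, exit in both arms.** Take 45% and 55% as the rates under full follow-up, and let the same share (20% to 45%) of stoppers in each arm be would-be responders.

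- Stopping 10% CSA, 5% RTX: shift +1.0 to +2.25 points; power 83.6% to 87.1%.
- Stopping 5% CSA, 10% RTX: shift -1.0 to -2.25 points; power 77.2% to 72.8%.
- Stopping 5% in both: no shift.

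**The case against.** The strongest reply is that the texts can be largely reconciled for CSA. Scenario 3 is specific and mandatory, and a specific rule normally overrides a general one. That has force, and it narrows the open conflict mainly to the RTX arm. It does not settle the matter, because the scenarios are introduced for temporary interruptions and a site could still apply the exit sentence to a permanent stop for intolerance.

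Second, scoring intolerance as failure is a legitimate composite strategy. This stands. The objection here is that the documents do not choose it clearly and elsewhere instruct the opposite.

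Third, follow-up may credit remissions produced by later therapy. This also stands, but the plan already accepts it for relapsers and for patients not in remission at month 12, who "will continue with the visit schedule, but the therapeutic/management plan will be solely at the discretion of the managing nephrologist".

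A reader might infer that the exit rule biases the trial towards non-inferiority because CSA is the less tolerable drug. The documents do not support a fixed direction. They give no intolerance rate for either arm; Toxicity of cyclosporine describes the common effects as usually tolerable or manageable; and the reading that scenario 3 governs CSA moves the result against RTX. Nor can the range be widened with other percentages in the text. The 13% reported beside the 39% belongs to the placebo arm of that trial, and the 60% in Sample size estimation is a 12-month RTX remission rate likened to that of calcineurin inhibitors, not a rescue rate.

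**Conclusion.** The conflict is real and reaches the primary endpoint, but for a small and precisely defined group. It is unresolved in the RTX arm and arguable in the CSA arm. Each reclassified patient is worth 1.6 points against the 15-point margin; the total size and the direction are unknown.

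The shifts of +3.1 and -2.75 points are illustrations, not bounds. They rest on assumed stopping rates and on borrowed response rates. The 39% follows a 26-week course with low-dose prednisone and was measured 12 months after stopping, whereas stopping before month 6 here leaves more than 18 months to the endpoint. The 55% describes a whole arm, not patients who stopped early.

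A claim that the type I error is inflated, or that the comparison is biased in favour of RTX, would go beyond what the documents show. This is a cheap improvement that removes an ambiguity in endpoint scoring and protects safety follow-up.

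**What to change.** - In Patient monitoring and evaluation, remove the intolerance limb of the exit sentence, so that only month-6 treatment failure leads to exit.
- State for both arms that patients who stop for intolerance stay on the scheduled visits to month 24, unless they meet the month-6 rule of less than 25% reduction.
- Score them in the ITT analysis on observed month-24 status, or month-18 status if month 24 is missing.
- Record any other immunosuppression after stopping study drug, with dates.
- Add two sensitivity analyses that score as failures (a) everyone who stopped for intolerance by month 6, which reproduces the exit reading, and (b) only those intolerance discontinuations who received other immunosuppression before the outcome visit.

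The cost is one deleted phrase, a short clarifying sentence, one dated data item and two extra analyses; the visits are already in the schedule. The downside is that the main analysis may credit some remissions due to rescue therapy. Analysis (b) shows how many among intolerance discontinuations; it does not address discretionary therapy in relapsers or month-12 non-remitters.

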1.1 Overview

This prospective, randomized, controlled phase III nephrology study will determine whether rituximab is non-inferior to cyclosporine in inducing long-term remission of proteinuria in patients with idiopathic membranous nephropathy (IMN.) Subjects are randomized to open-label courses of treatment: IV rituximab (RTX), 1000 mg (2 infusions, 14 days apart), or oral cyclosporine (CSA) 3.5 to 5 mg/kg/day. Subjects are evaluated at 6 months; those that meet treatment response criteria will continue study medication and receive either 2 further infusions of RTX or a further 6 months of daily CSA treatment. Throughout the study period, laboratory and safety parameters will be collected and documented.

Study Hypothesis: B cell targeting with Rituximab is non-inferior to Cyclosporine in inducing long-term remission of proteinuria.

Comparison(s): IV rituximab (RTX), 1000 mg (2 infusions, 14 days apart; repeated at 6 months if a substantial reduction in proteinuria (equal to or >25%) is seen at 6 months) or oral cyclosporine (CSA) 3.5 to 5 mg/kg/day for 6 months (continued for another 6 months if a substantial reduction in proteinuria (equal to or >25%) is seen at 6 months).

SPECIFIC AIMS:

The specific aims of this Phase III trial are to test the hypothesis;

1. That B cell targeting with Rituximab is **non-inferior to** Cyclosporine in inducing **long-term remission** (complete or partial) of proteinuria in patients with IMN.
2. That B cell targeting with Rituximab **reduces the number of relapses (efficacy in sustaining remission) and increases the time to relapse when compared with treatment with Cyclosporine.**
3. That B cell targeting with Rituximab is **as effective as** Cyclosporine in inducing **complete or partial remission** of proteinuria in patients with IMN during the active treatment phase.
4. That B cell targeting with Rituximab has a better side effect profile and improved quality of life when compared with treatment with Cyclosporine in patients with IMN.

BACKGROUND AND SIGNIFICANCE

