Rituximab: Patients randomized to the RTX arm will receive 1000 mg IV on Days 1 and 15. Patients who achieve complete remission at 6 months will not be retreated. A second course of RTX 1000 mg IV will be administered at study month 6 for individuals who have not achieved a complete remission, but have achieved at least a $\geq 25\%$ reduction compared to their central laboratory (Mayo Clinic Rochester) baseline (Time 0) proteinuria (but not a CR). Dosing at study month 6 will be independent of CD19/20+ B cell count. The rationale for retreating patients who have had an equal to or $> 25\%$ reduction in proteinuria at 6 months is based on our experience in our pilot studies (first study using 1000 mg on Days 1 and 15 and second study using 4 weekly doses of $375\text{mg}/\text{m}^2$) where an increase in the proteinuria remission rate was achieved after a second course of treatment. In our 2 studies repeated courses of RTX were not associated with additive adverse effects in comparison to their first course. If after six months the reduction in proteinuria is less than 25% compared to baseline the RTX treatment will not be repeated, the patient will exit from the study and will be considered a failure of therapy.

Dosage and Administration of Rituximab: The first infusion of both courses (Day 1 and Day 181) of RTX will be administered IV at an initial rate of 50 mg/hr. All patients

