Cyclosporine: Neoral brand (Novartis) is the preferred Cyclosporine product for this trial. Participating sites must contact the DMCC *prior* to dispensing any other brand to study participants as not all brands of Cyclosporine are bio-equivalent. Patients randomized to the Cyclosporine arm will be started at a dose of CSA = 3.5 mg/kg/day p.o. divided into 2 equal doses given at 12 hour intervals. Target trough CSA blood levels, as determined in whole blood by HPLC, are 125 to 175 ng/ml. Patients will have their doses adjusted according to their blood levels of CSA as monitored every 2 weeks +/- 3 days until the target trough level is reached. After reaching target, CSA trough levels will continue to be checked as per the visit schedule (Table 2a). If a complete remission is achieved by six months, CSA will be tapered by approximately 1/3 of the maintenance dose monthly and hence discontinued after two months. If there has been at least an equal to or >25% reduction compared to their central laboratory (Mayo Clinic Rochester) baseline (Time 0) proteinuria (but not complete remission) the CSA will be continued for an additional six months. A persistent and otherwise unexplained increase in serum creatinine >30% will prompt an approximate 25% dose reduction of CSA, aiming for a corresponding 25% reduction in CSA trough level (for example, if trough

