cyclosporine. If tolerated clinically and, as evidenced by the lack of persistent elevation of liver transaminase >3 times upper limit of normal or high CK, or clinical rhabdomyolysis, the dose will be increased according to the recently published KDOQI-dyslipidemia guidelines.⁸³ The dose should not be increased above the maximum of 40 mg/day. The rationale for not using a higher statin dose is because of the risk of developing proteinuria with the use of statins at high doses, and the added risk of rhabdomyolysis in the CSA group. Patients will remain at the highest tolerated dose for the entire duration of the study. Serum lipids will be measured at Time 0 and every 3 months thereafter. High sodium intake (e.g. >200 mm Na/d or 4.6 g sodium/d) can significantly impair the beneficial effects of Ang II blockade.⁸⁴ Therefore patients will be instructed to follow a low salt diet (2-3g/day). Patients will also receive dietary counseling at enrollment as part of their standard of care. Patients will be advised of a dietary protein target intake of 0.8-1.0 g/kg ideal body weight/day of high quality protein and will be encouraged to maintain the same diet throughout the duration of the study. Patients with proteinuria >10 g/24h and serum albumin <2 g/dl should be considered for prophylactic anticoagulation.

Patients randomized to receive Rituximab should be started on single strength Bactrim one a day (or its equivalent) for pneumocystis pneumonia prophylaxis. This treatment will continue until the end of the study treatment phase (12 months) and the B cells (CD19/20+) have been repleted (>15 cells/microliter on peripheral blood flow cytometry). B cells (CD19/20+) are expected to be replete by Month 12. In the rare event that B cells (CD19/20+) are not replete by Month 12, flow cytometry should be repeated at Month 18 (see table 2b) and Bactrim (or its equivalent) continued to that point of repletion.

Stopping points for medications:

1. For Cyclosporine: At 6 months, patients in complete remission (as previously defined) will have CSA dose tapered and discontinued while those who fail therapy will have CSA discontinued immediately (no need to taper the dose).
After 12 months of therapy, regardless of the degree of proteinuria, Cyclosporine will be tapered and discontinued as described above.
2. Patients in the RTX arm who have either failed therapy or are in complete remission at 6 months (as previously defined) will not have a repeat treatment course.

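### Dosing rules for patients in complete remission conflict at month 6 in both arms, and between months 6 and 12 on cyclosporine

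*Combined protocol and SAP*

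**What the plan says.** **Month-6 rule without a CR exception.** Section 1.1 Overview says that patients who meet the response criteria "continue study medication and receive either 2 further infusions of RTX or a further 6 months of daily CSA treatment". Overall Research Design and Methods sets the threshold at a 25% or greater reduction in proteinuria. Rituximab patients who reach it "will be given another identical course of RTX (1g x 2"), and on cyclosporine (CSA) it will "dictate continuation of the CSA for an additional 6 months (total of 12 months of full dose CSA"). Neither section exempts CR. The regimens named under Sample size estimation (rituximab repeated at month 6; CSA for 12 months plus a 2-month taper) carry no exemption either.

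**Month-6 rule with a CR exception.** The Rituximab paragraph says "Patients who achieve complete remission at 6 months will not be retreated" and limits the second course to patients not in CR. The Cyclosporine paragraph says "If a complete remission is achieved by six months, CSA will be tapered by approximately 1/3 of the maintenance dose monthly", ending after two months, and limits the six-month extension in the same way. Stopping points for medications, items 1 and 2, repeats both rules.

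**CR at an unstated time.** Patient monitoring and evaluation says "Patients who go in to complete remission will discontinue study drug but will continue with full visit follow-ups until month 24 as scheduled". It names no visit and no measurement, and it leaves further management to the treating nephrologist. Stopping points, item 1, says "After 12 months of therapy, regardless of the degree of proteinuria, Cyclosporine will be tapered and discontinued as described above".

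**The concern.** A site can follow one section faithfully and break another. The trial is open-label, so different sites, or the same site for different patients, could settle the conflict differently.

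The rule decides how long a CSA patient has been off drug at the month-24 primary assessment, and whether a rituximab patient has had one course or two. The sample size section expects relapse of up to 50% once CSA stops. If more time off drug means more relapse, earlier stopping lowers the CSA response rate and makes non-inferiority easier to show. Rituximab dosing is over by about Day 195, so any uncertainty between months 6 and 12 bears on the CSA arm alone.

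The per-protocol set is restricted to patients who received their whole course and were seen at month 24. If the length of the course is unclear for CR patients, so is their membership of that set. That matters in a non-inferiority trial.

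**Working it through.** **1. The plan's own figure.** With 55% (rituximab), 45% (CSA), a 15-point margin, one-sided alpha 0.025 and 80% power:

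n per arm = [0.55×0.45 + 0.45×0.55] × (1.960 + 0.842)² / (0.55 − 0.45 + 0.15)² = 62.16, rounded up to 63.

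This reproduces the stated 63, and power at 63 is 80.5%. The point below does not change it.

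**2. Does a CR patient meet the 25% rule?** Entry requires at least 5 g/24h. CR (Table 1) requires at most 0.3 g/24h, with an albumin criterion. The smallest possible reduction is 1 − 0.3/5 = 94%. So every patient in CR also meets the continuation rule as the Overview and the design section word it.

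**3. Exposure for CR at month 6 under each wording.**

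| | Overview and Overall Research Design, read literally | Rituximab and Cyclosporine paragraphs, Stopping points |
|---|---|---|
| Rituximab | 4 infusions, 4000 mg | 2 infusions, 2000 mg |
| CSA off drug | 12 + 2 = month 14 | 6 + 2 = month 8 |
| Time off CSA before month 24 | 24 − 14 = 10 months | 24 − 8 = 16 months |

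**4. CR first seen between months 6 and 12 on CSA.** Table 2a schedules a single 24-hour urine protein and a serum albumin at month 9, so a site can see a result that fits the CR criteria. The unqualified sentence in Patient monitoring and evaluation then stops CSA. The Cyclosporine paragraph and Stopping points continue it to month 12 and then taper, which leaves 10 months off drug. If the same two-month taper were used from month 9 (an assumption, since no taper is given for that case), CSA would end at month 11, leaving 24 − 11 = 13 months. Laboratory testing sets remission status from the mean of two collections at Time 0 and months 6, 12, 18 and 24 only, but the monitoring sentence does not refer to that rule.

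**5. Size for CR at month 6 on CSA.**
- The Remission Cohort section calls CR by month 6 rare.
- The earlier placebo-controlled CSA trial in the Background had 75% in remission at 26 weeks, 10% of them complete. Applied here as an assumption: 0.75 × 0.10 × 63 = 4.7, about 5 patients.
- The Remission Cohort section expects 20–30% relapse after CR at month 6: 4.7 × 0.20 = 0.9 and 4.7 × 0.30 = 1.4, so about 1 to 1.4 patients.
- As a share of 63: 1.5% to 2.3%.

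This assumes that nobody relapses under the other reading, and the 20–30% covers a window that runs to month 36. Both push the figure up. The documents give no count for CR in months 6–12 on CSA and no 6-month CR rate for rituximab.

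**The case against.** The strongest reply is that these are incomplete summaries rather than rival rules. The two treatment paragraphs and the Stopping points list agree with one another for CR at month 6. The sampling schedule also treats CR at month 6 as its own track, through the footnotes to Tables 2a and 2b and the Remission Cohort section. A site dosing from the treatment paragraphs meets an explicit CR rule. As for months 6–12, remission status is formally set only at the paired-collection visits, so month 6 is the only scheduled CR determination before month 12, when CSA is tapered whatever the proteinuria.

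Much of this stands and limits the point. It does not remove it. The design section states its rule as operative, not as an outline, and the monitoring sentence does not tie itself to the paired collections.

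A reader might infer more than the documents support:

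- **That a CR patient on CSA may be stopped at once.** No section says so. Stopping points reserves immediate stopping for treatment failures, and the word discontinue in the monitoring section is compatible with a taper that ends in discontinuation.
- **That the Cyclosporine paragraph and Stopping points differ over a CR at month 3.** Their wordings, by six months and at six months, describe the same decision visit, and month 3 is a single collection.
- **That 4 to 8 points of the 15-point margin are at risk.** That takes 50% relapse on one reading, none on the other, and 5 to 10 patients (0.5 × 5 = 2.5 and 0.5 × 10 = 5 of 63). It passes over the lower relapse rate given for CR at month 6 and doubles the patient count without a source. Zero relapse is not credible when every reading leaves patients off CSA for at least 10 months before month 24.

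**Conclusion.** Two conflicts stand. For CR at month 6, the Overview and design section literally give 4 infusions and CSA to month 14, against 2 infusions and CSA to about month 8 elsewhere. For CR first found between months 6 and 12 on CSA, the monitoring section stops the drug with no time point, while other sections continue it to month 12.

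The likely effect on the primary result is small: about 1 to 1.4 CSA patients, or 1.5 to 2.3 percentage points, for CR at month 6. This rests on carrying over the 7.5% CR rate from the earlier trial, on the plan's 20–30% relapse figure, and on no relapse under the other reading. The months 6–12 group and the rituximab arm cannot be sized from the documents. The sample size is unaffected.

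The point is still worth acting on, because contradictory dosing text in an open-label trial leaves exposure to site choice and per-protocol membership unclear for CR patients. This review takes no view on which dosing rule is right.

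**What to change.** Reconcile the Overview, Overall Research Design, the Rituximab and Cyclosporine paragraphs, Patient monitoring and evaluation, Stopping points, and the regimen description under Sample size estimation into one rule per arm. The rule should state the visit or visits at which CR changes dosing, and the measurement that establishes CR there (paired central-laboratory collections or a single local one). It should make clear what happens to a CSA patient whose CR first appears between months 6 and 12. The sponsor's clinicians choose the rule.

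In the Statistical and Analytical Plan, state what counts as a complete course for patients in CR, so that per-protocol membership is fixed before the data are seen.

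The cost is amendment wording, with no added visits, tests or patients.
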